### Creatine Kinase (CK)

The CK data in U/L did not follow a normal distribution, and a logarithmic transformation ( $\log_{10}$ ) was applied. After the transformation, the data showed a normal distribution and homogeneity of variances for conducting parametric tests. Repeated measures ANOVA revealed a moment interaction ( $F_{2,27} < 0.001$ ) and a moment versus treatment interaction ( $F_{2,27} < 0.001$ ). Tukey's post hoc test identified significant differences as shown in the table below:

[figure not shown]
**Table 5.** Mean values ( $\pm$ standard deviation) of creatine phosphokinase (CK) in U/L for the Sham, PBM-pre, and PBM-post groups at pre, 24h, 48h, and 72h after the muscle damage induction protocol:

| Groups   | CK pre                 | CK 24h                  | CK 48h                  | CK 72h                  |
|----------|------------------------|-------------------------|-------------------------|-------------------------|
| Sham     | 289.2 ( $\pm 209.94$ ) | 661.5 ( $\pm 477.24$ )* | 491.6 ( $\pm 285.44$ )* | 523.2 ( $\pm 343.15$ )* |
| PBM-pre  | 249.2 ( $\pm 112.28$ ) | 372.7 ( $\pm 190.58$ )  | 424.2 ( $\pm 248.90$ )  | 392.6 ( $\pm 215.23$ )  |
| PBM-post | 287.8 ( $\pm 199.09$ ) | 794.5 ( $\pm 763.80$ )* | 631.2 ( $\pm 512.08$ )* | 271.44 ( $\pm 133.27$ ) |

**Abbreviations:** PBM (photobiomodulation); CK (creatine phosphokinase). \* p-value  $< 0.05$  in two-way repeated measures ANOVA followed by Tukey's post hoc analysis.

Compared to the pre-moment of the muscle damage induction protocol, there was a significant increase in CK levels in the Sham group ( $p = 0.001$ ) and PBM-post group ( $p = 0.001$ ) at the moment 24h after, while in the PBM-pre group the increase was not significant ( $p = 0.285$ ). When comparing the pre-moment of the muscle damage induction protocol to 48h after, the Sham group had a significant increase in CK ( $p = 0.028$ ), as well as the PBM-post group ( $p = 0.015$ ), while the PBM-pre group did not show a significant increase ( $p = 0.131$ ). In the

comparison between the pre-moment of the muscle damage induction protocol and 72h after, only the Sham group had a significant increase in CK ( $p = 0.010$ ), while the PBM-pre and PBM-post groups did not show significant increases ( $p = 0.506$ ;  $p = 1.000$ , respectively). In the comparison between groups for the respective CK assessment moments, there were no significant differences ( $p > 0.05$ ). The graphical representation of these results is in Figure 4.

**Figure 4.** Results for creatine phosphokinase (CK) at the evaluated time points (pre-moment of muscle damage induction protocol, 24h, 48h, and 72h after), and experimental groups (Sham, PBM-pre, PBM-post). Values presented in both log10-transformed and raw formats. Data expressed as mean ( $\pm$  standard error).

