## Title page

# **Whole-body photobiomodulation for muscle performance enhancement, attenuation of muscular damage and delayed onset muscle soreness in professional soccer athletes – randomized sham-controlled trial**

## Abstract

**Context:** Photobiomodulation (PBM) has recently been applied in sports to enhance physical performance and mitigate muscle damage and delayed-onset muscle soreness (DOMS). These effects may be particularly relevant when PBM is delivered to large body areas through whole-body irradiation. **Objective:** To evaluate the effects of whole-body PBM on muscle damage, DOMS, and muscle performance in professional soccer athletes undergoing a muscle damage induction protocol. **Methods:** A randomized, double-blind, sham-controlled trial was conducted with 30 professional soccer players from a Brazilian team. Participants were randomly allocated into three groups ( $n = 10$  each): (a) PBM-post, (b) PBM-pre, and (c) PBM-sham. Outcomes included serum creatine kinase (CK) levels, DOMS (numeric rating scale [NRS] and pain mapping [mapDOMS]), muscle performance (squat jump [SJ] and countermovement jump [CMJ]), and isometric dynamometry of the knee extensors. All groups received PBM irradiation (active or sham), followed by the muscle damage induction protocol, and subsequent PBM irradiation (active or sham). Assessments were performed at baseline, 24 h, 48 h, and 72 h post-induction. **Results:** CK levels significantly increased ( $p < 0.05$ ) at 24–72 h in the sham group and at 24–48 h in the PBM-post group. In contrast, the PBM-pre group showed no significant increase ( $p > 0.05$ ) across 24–72 h. For DOMS (NRS), the sham group

reported significant increases ( $p < 0.05$ ) from 24–72 h, the PBM-pre group only at 24 h, and the PBM-post group at no time point. DOMS assessed by mapDOMS showed no significant changes ( $p > 0.05$ ) across groups or time points. No significant differences ( $p > 0.05$ ) were observed in muscle performance outcomes among groups. **Conclusion:** Pre-exercise PBM provided protective effects against muscle damage (lower CK) and reduced DOMS at 48–72 h, while post-exercise PBM reduced DOMS consistently at all time points (24–72 h). Neither pre- nor post-exercise PBM improved or worsened muscle performance.

**Keywords:** CK; DOMS; light-emitting diode; low-level laser therapy; recovery

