## Randomization and Allocation Concealment

The randomization was conducted using the website randomization.com, and the participants were allocated into three groups of ten individuals each. To ensure allocation concealment, sealed opaque envelopes were used, containing the randomly assigned interventions: PBM-post, PBM-pre, and PBM-Sham. Only one researcher (therapist 1) was involved in this process, being responsible for applying PBM to all participants. This researcher was blinded to the other assessments in the study, which were conducted by therapist 2. Participants were unaware of which intervention was applied during the study.

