### STATISTICAL ANALYSIS PLAN (SUMMARY)

Primary endpoint: Serum CK levels (U/L) over time.

Secondary endpoints: DOMS (NRS and mapDOMS), SJ and CMJ jump heights (cm), and isometric knee extensor force (kgf).

Statistical tests:

- Normality (Shapiro–Wilk) and homogeneity (Levene).
- Two-way repeated measures ANOVA with Tukey post hoc (parametric).
- Friedman and Kruskal–Wallis (nonparametric when assumptions not met).
- Significance level:  $\alpha = 0.05$ .

Software: IBM SPSS Statistics v20.0.

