## Data Analysis

Data analysis was conducted by a researcher blinded to participant group allocation. The primary outcome of the study was considered the muscle damage measured by CK levels.

The data were descriptively analyzed using mean and standard deviation. The independent variables were the experimental conditions (Sham, PBM-pre, and PBM-post) and assessment times pre, 24h, 48h, 72h after the muscle damage induction protocol. Normality and homoscedasticity assumptions were tested beforehand using the Shapiro-Wilk W Test and Levene test, respectively. The dependent variables included CK, DOMS, height of jumps in Squat Jump (SJ) and Counter Movement Jump (CMJ), and isometric manual dynamometry of the femoral quadriceps (kgf).

Two-way repeated measures analysis of variance (ANOVA) was conducted (considering pre, 24h, 48h, and 72h after the muscle damage induction protocol) followed by Tukey's post hoc test when the data showed normal distribution and variance homogeneity. In cases where the data did not present normal distribution, a logarithmic transformation (log10) was adopted, and normality and variance homogeneity were verified again for parametric tests. If the data did not meet the assumptions of normality and variance homogeneity, non-parametric tests such as Friedman's ANOVA (intragroup analyses) and Kruskal-Wallis (intergroup analyses) were employed. The significance level was set at 5%. Statistical analysis was performed using a statistical software (SPSS Statistics for Windows version 20.0, IBM, Chicago, IL, United States).

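### PBM-pre's non-significant CK rises depend on an unstated, very wide Tukey family and cannot support the protection claim

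*Combined protocol and SAP*

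**What the plan says.** The Statistical Analysis Plan (Summary) makes serum CK over time the primary endpoint and lists "Two-way repeated measures ANOVA with Tukey post hoc (parametric") at a 5% level. Data Analysis repeats this, with Tukey as the "post hoc test when the data showed normal distribution and variance homogeneity", the time factor "considering pre, 24h, 48h, and 72h after the muscle damage induction protocol", and a log10 transformation where normality fails. Neither section says which pairs of means Tukey covers.

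The Creatine Kinase (CK) results give nine p-values against the pre value, three per arm. For PBM-pre they are 0.285 at 24 h ("while in the PBM-pre group the increase was not significant"), 0.131 at 48 h and 0.506 at 72 h ("while the PBM-pre and PBM-post groups did not show significant increases"). The same section then says that no comparison between groups at any CK time point was significant.

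The Abstract carries the within-arm result forward ("In contrast, the PBM-pre group showed no significant increase") and concludes that pre-exercise PBM protected against muscle damage, with lower CK given as the reason.

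**The concern.** A wide multiplicity family usually makes a trial harder to win. Here it works the other way, because the Abstract counts non-significance in an active arm as benefit: the more pairs Tukey has to cover, the easier it is to report that PBM-pre showed no increase. If the family is all 66 pairs, 36 of them compare different arms at different times and answer no question the report asks.

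At stake is the headline conclusion on the primary endpoint. With no between-arm CK difference reported, the pattern of significant rises in two arms and none in the third is the only post hoc support stated for protection by PBM-pre.

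**Working it through.** **1. Which family was run?** "the participants were allocated into three groups of ten individuals each", measured at four times, gives 3 × 4 = 12 cells, 12 × 11 / 2 = 66 pairs and 27 × 3 = 81 within-subject error df. Of the 66 pairs, 3 × 6 = 18 are within an arm, 4 × 3 = 12 are between arms at one time, and 66 − 18 − 12 = 36 are neither.

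The NRS was analysed untransformed, so its p-values can be inverted. For a change d with Tukey p-value p over k means, solve P(Q(k, 81) > q) = p; the implied error mean square is 10 × (d/q)². One analysis must give one value. Changes come from Table 6 and p-values from the text after it.

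| Change (p) | k = 12 | k = 4 | k = 3 |
|---|---|---|---|
| 2.6 (0.027) | 2.636 | 4.1 | 4.9 |
| 1.7 (0.460) | 2.646 | 6.7 | 10.1 |
| 1.6 (0.555) | 2.646 | 7.4 | 11.9 |
| 1.1 (0.933) | 2.647 | 17.0 | 48.0 |

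Of these, only k = 12 gives a constant. The Table 6 means with the printed interaction p of 0.044 give 2.644, which agrees. Fixing the standard error at 2.6 → 0.027, k = 9 already misses: it predicts 0.398 for a change of 1.7, against 0.460 printed and 0.457 for k = 12.

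**2. The CK p-values under that family.** Data Analysis prescribes one Tukey procedure for all outcomes. With k = 12 and 81 df, t = q/√2:

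| PBM-pre vs pre | Printed p | q | t(81) | Unadjusted p |
|---|---|---|---|---|
| 24 h | 0.285 | 3.709 | 2.62 | 0.0104 |
| 48 h | 0.131 | 4.227 | 2.99 | 0.0037 |
| 72 h | 0.506 | 3.210 | 2.27 | 0.0259 |

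**3. Narrower families.** The five significant sham and PBM-post comparisons invert to smaller p-values (largest 0.0006, sham 48 h), so PBM-pre 48 h, 24 h and 72 h rank sixth, seventh and eighth of nine. Holm multiplies by 4, 3 and 2: 4 × 0.0037 = 0.015, 3 × 0.0104 = 0.031, 2 × 0.0259 = 0.052.

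| Method, nine within-arm comparisons | 24 h | 48 h | 72 h |
|---|---|---|---|
| Holm or Hochberg | 0.031 | 0.015 | 0.052 |
| Single-step Dunnett-type (simulated) | 0.081 | 0.030 | 0.186 |
| Sidak | 0.090 | 0.033 | 0.210 |
| Bonferroni | 0.094 | 0.033 | 0.233 |

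The report also reads 3 pairs × 4 times = 12 between-arm comparisons, so 9 + 12 = 21. If none of those 12 has a smaller unadjusted p, Holm over 21 gives 16 × 0.0037 = 0.059 at 48 h and 15 × 0.0104 = 0.156 at 24 h. Bonferroni gives 0.078 and 0.219.

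**4. Size of the rise.** Raw PBM-pre means go from 249.2 to 372.7, 424.2 and 392.6 U/L: +50%, +70% and +58%. With a lognormal approximation to Table 5 (log variance s² = ln(1 + SD²/mean²), log mean = ln(mean) − s²/2), the log means are 5.426 at baseline and 5.805, 5.902 and 5.841 afterwards. The geometric ratios to baseline are about 1.46, 1.61 and 1.52.

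**5. The contrast that bears on protection.** The same approximation, with an assumed log10 error mean square of 0.025 to 0.031, gives PBM-pre versus sham ratios of change of 0.64 at 24 h (p 0.055 to 0.084; 95% CI from 0.40–1.01 to 0.38–1.06), 0.89 at 48 h (p about 0.6) and 0.81 at 72 h (p about 0.4).

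**The case against.** The statement about PBM-pre correctly reports the test that the plan names. Tukey over all cell means is an ordinary reading of that plan, no smaller family was promised, and choosing Holm over nine comparisons once the p-values are known is itself a post hoc choice. This stands. A reader might infer that the headline is simply wrong and that PBM-pre rose significantly at both 24 h and 48 h. The documents do not support that: 24 h fails under three of the nine-comparison methods, and the report reads 21 CK comparisons, over which neither time is significant. Within-arm Dunnett (0.028 at 24 h) corrects for only three comparisons, so it does not settle the matter.

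The family is also less secure for CK than for NRS. CK log means and error mean square are not printed. Inverting the CK p-values at k = 12 with the lognormal approximation gives error mean squares from about 0.020 to 0.035, and values of 0.025 to 0.031 imply an interaction p of about 0.003 to 0.012, not the printed value below 0.001. The approximation is crude, so this does not refute k = 12, but CK does not confirm it independently. Had Tukey covered only four means, PBM-pre would be non-significant in a small family; the implied interaction p would then be about 0.11, further still from the printed value.

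Finally, family size cannot settle whether PBM-pre differs from sham. By the same approximation the 24 h rise is about 1.46-fold in PBM-pre and 2.29-fold in sham, so a possible difference should not be dismissed either. That is a between-arm question.

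**Conclusion.** The concern holds in this form. PBM-pre's non-significance is accurately reported, but it depends on a family the plan never states and which, on the NRS evidence, was very wide. It is not evidence that CK stayed level: unadjusted p-values are about 0.010, 0.004 and 0.026, and the approximate rises are 1.46, 1.61 and 1.52 times baseline. At 48 h the rise is significant over the nine within-arm comparisons by every method tried; at 24 h the answer turns on the method; at 72 h it is not significant. Neither 24 h nor 48 h is significant over all 21 by Holm.

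A result that changes with an unstated choice, alongside no between-arm CK difference at any time, cannot carry the Abstract's protection claim. That claim must be changed. Replacing Tukey as the main analysis is not required.

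Assumptions: CK used the same Tukey procedure as NRS; error is pooled across arms with 81 df. With 27 df the nine-comparison pattern at 24 h and 48 h is unchanged (Holm 0.037 and 0.017; Bonferroni 0.110 and 0.039). The ratios rest on the lognormal approximation, and a rerun on the data should replace them.

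**What to change.** - **Abstract:** withdraw the statement that pre-exercise PBM protects against muscle damage in so far as it rests on non-significance within PBM-pre. Base the CK conclusion on arm-by-time contrasts: change from pre, each PBM arm versus sham, on log CK, with 95% CIs.
- **Statistical Analysis Plan (Summary) and Data Analysis:** state the family over which Tukey was applied.
- **Creatine Kinase (CK) results and Table 5:** add the ratio to baseline with 95% CI for each arm and time. Show the nine within-arm comparisons under Holm as a sensitivity analysis, labelled post hoc.

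The cost is one rerun on existing data, some rewording, and a less favourable headline for PBM-pre.

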#### Delayed Onset Muscle Soreness (DOMS) measured by the Numeric Rating Scale (NRS).

Repeated measures ANOVA revealed a moment interaction ( $F_{2,27} < 0.001$ ) and a moment versus treatment interaction ( $F_{2,27} = 0.044$ ). Tukey's post hoc analysis identified significant differences as shown in Table 6.

[figure not shown]
**Table 6.** Mean values ( $\pm$  standard deviation) of Delayed Onset Muscle Soreness (DOMS) measured by the Numeric Rating Scale (NRS) for the Sham, PBM-pre, and PBM-post groups at pre, 24h, 48h, and 72h after the muscle damage induction protocol:

| Groups | DOMS (NRS)          | DOMS (NRS)           | DOMS (NRS)           | DOMS (NRS)           |
|--------|---------------------|----------------------|----------------------|----------------------|
|        | pre                 | 24h                  | 48h                  | 72h                  |
| Sham   | 0.60 ( $\pm 1.26$ ) | 5.70 ( $\pm 2.05$ )* | 4.20 ( $\pm 2.39$ )* | 3.20 ( $\pm 2.78$ )* |

|                 |                     |                      |                     |                     |
|-----------------|---------------------|----------------------|---------------------|---------------------|
| PBM-pre  | 1.20 ( $\pm 1.61$ ) | 3.80 ( $\pm 2.74$ )* | 2.80 ( $\pm 1.54$ ) | 1.70 ( $\pm 1.82$ ) |
| PBM-post | 1.30 ( $\pm 2.11$ ) | 3.00 ( $\pm 2.00$ )  | 2.40 ( $\pm 1.83$ ) | 2.10 ( $\pm 1.72$ ) |

**Abbreviations:** PBM (photobiomodulation); DOMS (Delayed Onset Muscle Soreness); NRS (Numeric Rating Scale); \* p-value < 0.05 in two-way repeated measures ANOVA followed by Tukey's post hoc analysis.

Compared to the pre-moment of the muscle damage induction protocol, there was a significant increase in DOMS measured by the NRS in the Sham group ( $p < 0.001$ ) and PBM-pre group ( $p = 0.027$ ) at the moment 24h after, while the PBM-post group did not show a significant increase ( $p = 0.460$ ). In the comparison between the pre-moment of the muscle damage induction protocol and 48h after, the Sham group had a significant increase in DOMS (NRS) ( $p < 0.001$ ), while the PBM-pre and PBM-post groups did not show significant increases ( $p = 0.555$ ;  $p = 0.933$ , respectively). In the comparison between the pre-moment of the muscle damage induction protocol and 72h after, only the Sham group had a significant increase in DOMS ( $p = 0.027$ ), while the PBM-pre and PBM-post groups did not show significant increases ( $p = 0.999$ ;  $p = 0.993$ , respectively). In the comparison between groups for the respective moments of DOMS (NRS) assessment, there were no significant differences ( $p > 0.05$ ). The graphical representation of these results is in Figure 5.

**Figure 5.** Results for Delayed Onset Muscle Soreness (DOMS), measured by the Numeric Rating Scale (NRS) at the evaluated time points (pre-moment of muscle damage induction protocol, 24h, 48h, and 72h after), and experimental groups (Sham, PBM-pre, PBM-post). Data expressed as mean ( $\pm$  standard error).

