### **c) Delayed Onset Muscle Soreness (DOMS):**

The perception of Delayed Onset Muscle Soreness (DOMS) was assessed using the Numeric Rating Scale (NRS). The scale was numbered from 0 to 10, where 0 indicated the absence of muscle pain, and 10 indicated maximum muscle pain during a maximum voluntary contraction for knee extension in a seated position. The choice of NRS was based on its reliability and responsiveness, as reported by .

[figure not shown]
The location and extent (percentage area) of DOMS were assessed using a pain map (mapDOMS) using a body chart representing the human body from different views (frontal, lateral, and dorsal). Two variables, the extent and location of pain, were used following the approach proposed by . Briefly, the areas where athletes reported pain were marked and later measured in cm. The painted area was then calculated using ImageJ software, an open-source software created by Wayne Rasband at the National Institutes of Health (NIH) in 1987 . Finally, the painted area was calculated as a percentage (%) of the total area related to the lower limbs.

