## RESULTS

Thirty male professional football players (high level) from the same team were recruited and completed all procedures of this study. Therefore, there were no dropouts, and intention-to-treat analysis was not necessary. Anthropometric data are described in Table 4. No adverse effects were reported during the study.

**Table 4.** Anthropometric data of the investigated athlete sample. Values in mean ( $\pm$  standard deviation):

| Groups | Age (years)  | Body Mass (kg) | BMI
(kg/m^2) | Years of Practice | Fitzpatrick
Phototype          |
|---------------|---------------------|-----------------------|-----------------------------------|--------------------------|-------------------------------------------|
| Sham   | 18.70 ( $\pm$ 0.82) | 76.03 ( $\pm$ 13.27)  | 22.62 ( $\pm$ 2.10)               | 9.60 ( $\pm$ 1.77)       | Type I: 2,
Type II: 0,
Type III: 3, |

|                 |                      |                      |                      |                      |                                                                       |
|-----------------|----------------------|----------------------|----------------------|----------------------|-----------------------------------------------------------------------|
|                 |                      |                      |                      |                      | Type IV: 3,
Type V: 2                                              |
| PBM-pre  | 20.50 ( $\pm 4.30$ ) | 70.43 ( $\pm 4.90$ ) | 23.07 ( $\pm 0.94$ ) | 11.30 ( $\pm 3.74$ ) | Type I: 2,
Type II: 2,
Type III: 3,
Type IV: 2,
Type V: 1 |
| PBM-post | 21.22 ( $\pm 7.44$ ) | 76.13 ( $\pm 8.03$ ) | 23.48 ( $\pm 1.73$ ) | 11.44 ( $\pm 3.46$ ) | Type I: 3,
Type II: 5,
Type III: 1,
Type IV: 1,
Type V: 0 |

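### NRS soreness was analysed by raw-scale ANOVA and Tukey with no reported assumption check, although the baseline scores, judged by arm, fail the plan's normality rule and make its non-parametric tests due

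*Combined protocol and SAP*

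**What the plan says.** The Data Analysis section sets a sequence. First, "Normality and homoscedasticity assumptions were tested beforehand using the Shapiro-Wilk W Test and Levene test". Two-way repeated measures ANOVA with Tukey follows when both assumptions hold. Non-normal data are log10-transformed and re-tested. Then: "If the data did not meet the assumptions of normality and variance homogeneity, non-parametric tests" are used, namely Friedman within arms and Kruskal-Wallis between arms. The SAP summary repeats the fallback. On alpha, "The significance level was set at 5" per cent; no adjustment across time points is given.

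The Results say for CK and for mapDOMS that normality failed and that log10 was applied. The NRS section has no such statement. It goes straight to repeated measures ANOVA, with "a moment versus treatment interaction ( $F_{2,27} = 0.044" (a p-value printed as an F), and to Tukey comparisons. It ends: "In the comparison between groups for the respective moments of DOMS (NRS) assessment, there were no significant differences".

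The abstract concludes that pre-exercise treatment reduced soreness at 48–72 h and post-exercise treatment at all times from 24 to 72 h.

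**The concern.** Baseline NRS means are 0.60, 1.20 and 1.30 on a scale starting at 0, and each SD exceeds its mean. Such scores pile up at zero and are unlikely to pass Shapiro-Wilk. If they fail, the plan leads to log10, which is undefined at zero, and then to rank tests. None of this is reported for NRS.

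Two things are at stake. The reported NRS analysis may not be the one the plan prescribes. And the prescribed between-arm test compares three arms at one time, so it need not agree at every time with the reported finding of no between-arm difference.

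**Working it through.** **Inputs.** Arms: "the participants were allocated into three groups of ten individuals each". Completeness: "there were no dropouts, and intention-to-treat analysis was not necessary". Scale: "The scale was numbered from 0 to 10". Means and SDs are from Table 6. Whole-number scoring is an assumption.

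**1. Reproducing the reported analysis on the raw scale.**
- Arm means over the four times are 3.425, 2.375 and 2.200; time means are 1.033, 4.167, 3.133 and 2.333; the grand mean is 2.667.
- Interaction SS = 10 × Σ(cell − arm − time + grand)² = 36.15 on (3−1)(4−1) = 6 df, so MS = 6.025.
- The error MS is not printed. Solving from the Tukey values (12 means, 27 × 3 = 81 df) gives about 2.645.
- F = 6.025/2.645 = 2.278 on 6 and 81 df, p = 0.0441. Printed: 0.044.
- With the same error term, SE = √(2.645/10) = 0.514. Tukey p against baseline:

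| Contrast | Computed | Printed |
|---|---|---|
| Sham 48 h | 0.0002 | <0.001 |
| Sham 72 h | 0.0275 | 0.027 |
| PBM-pre 24 h | 0.0275 | 0.027 |
| PBM-pre 48 h | 0.555 | 0.555 |
| PBM-pre 72 h | 1.000 | 0.999 |
| PBM-post 24 h | 0.460 | 0.460 |
| PBM-post 48 h | 0.933 | 0.933 |
| PBM-post 72 h | 0.994 | 0.993 |

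One error term fits all of them to about 0.001, so the analysis was on untransformed scores.

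**2. Baseline normality by arm.** All sets of ten whole numbers from 0 to 10 that match the printed mean and SD (rounded or truncated) were listed:

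| Arm | Fitting sets | Zeros among 10 | Largest Shapiro-Wilk p, raw | Largest p, log10(x+1) |
|---|---|---|---|---|
| Sham | 2 | 7–8 | 0.00002 | 0.0002 |
| PBM-pre | 4 | 4–6 | 0.005 | 0.044 |
| PBM-post | 3 | 4–7 | 0.001 | 0.024 |

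Plain log10 cannot be computed for any of the nine sets. Adding 1 is not in the plan, and it fails as well. With non-integer scores allowed, a numerical search found raw-scale maxima of 0.00003, 0.014 and 0.001. All 30 baseline scores pooled also fail (p < 0.00001).

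**3. The planned between-arm test.** Tie-corrected Kruskal-Wallis over every combination of fitting sets:

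| Time | Combinations | Median p | 5th–95th percentile | Share below 0.05 |
|---|---|---|---|---|
| Baseline | 24 | 0.47 | 0.33–0.73 | 0 |
| 24 h | 114,660 | 0.038 | 0.017–0.067 | 79.8% |
| 48 h | 19,456 | 0.15 | 0.07–0.27 | 1.5% |
| 72 h | 5,005 | 0.39 | 0.24–0.53 | 0 |

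At 24 h the full range is 0.001 to 0.179. Below 0.05/4 = 0.0125 the share is 1.9%. As a check from the summary figures, one-way ANOVA at 24 h gives F = 19.23/5.237 = 3.67 on 2 and 27 df, p = 0.039.

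Friedman cannot be approximated in this way, because Table 6 does not show which scores belong to the same athlete.

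**The case against.** **The testing unit is not stated.** The plan does not say whether Shapiro-Wilk applies per cell, per time or to residuals. Pooled over all 120 cell residuals, about 6% of reconstructed data sets pass. Residuals of the repeated-measures model, which also remove the athlete effect, are more favourable: in 800 reconstructions matching Table 6 and the error term of 2.645, with scores linked across times at random (an assumption), 84% exceeded 0.05, median p about 0.3. This stands. A reader might infer that the data could not have passed in any form; the documents support that only for baseline scores, by arm or pooled.

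**The reported between-arm finding is not shown to be wrong.** A reader might infer from the 80% that it is. That figure is a share of equally weighted reconstructions, not a probability about the real data, and it is unadjusted. The reported statement also fits a Tukey test over 12 means with the pooled cell variance: the mean of the twelve squared SDs is 4.148, q = 2.7/√(4.148/10) = 4.19, and p for Sham versus PBM-post at 24 h is 0.13 to 0.17 for 108 down to 27 df. Using 2.645 would give q = 2.7/0.514 = 5.25, p = 0.018, but that is within-athlete error and does not suit a comparison between arms. The two tests ask different questions.

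**At 48 and 72 h nothing changes.** The report already finds no arm difference there. The abstract's claims at those times rest on significance within arms, which is a weakness whichever test is used.

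**NRS is secondary**, and nothing here shows that the interaction p of 0.044 is misleading.

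**Conclusion.** The concern holds in a limited form. NRS was analysed on the raw scale, and none of the steps the plan requires before or instead of ANOVA is reported. Judged by arm at baseline, normality fails in every whole-number data set consistent with Table 6, the log10 step does not rescue it, and Friedman and Kruskal-Wallis were due. If the rule was applied to residuals it may have passed, but that needs stating and showing.

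A between-arm difference at 24 h is possible, not established: median unadjusted p about 0.038, with about one fitting data set in five at or above 0.05 and about 2% below 0.0125. At 48 and 72 h the fallback would almost certainly agree with the report that no arm difference is significant.

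This rests on whole-number scoring (the raw-scale failure does not depend on it), on Table 6 being correctly printed, and on equal weight for each fitting data set. The individual scores would settle it.

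**What to change.** 1. State the NRS Shapiro-Wilk and Levene results and the unit tested (cell, time point or residual).
2. Report the planned Friedman test within each arm and Kruskal-Wallis between arms at each time, with a multiplicity adjustment over the time points. The plan names no adjustment, so say that it was added afterwards.
3. If the check failed, label the reported ANOVA and Tukey results as a departure from the plan.
4. Reword the abstract's soreness claims at 48–72 h to say that no between-arm difference was shown. Base any statement about 24 h on the adjusted result.
5. A randomisation test on each athlete's mean 24–72 h NRS minus baseline may be added only as a labelled post hoc sensitivity analysis. It would be chosen after the results were seen, and by averaging over times it cannot support claims about particular times.

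The cost is a few hours of re-analysis on complete data already held, plus edits to the NRS results and the abstract. Some statements become weaker; the 24 h comparison could become stronger.
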